9.1.4 Additional Extension Phase (Extension B)

Extension B will be open for subjects who reside in Japan or subjects residing in countries where an EAP cannot be implemented, and who in the opinion of the investigator continue to benefit from treatment with perampanel. Participation in Extension B will continue as long as clinically appropriate according to the judgment of the investigator until perampanel is commercially available. (revised per Amendment 04)

For subjects residing in countries where commercial perampanel is not yet available and EAP can be implemented (provided that a positive risk/benefit is demonstrated based on analysis of the Core Study data), subjects who have completed Extension A and who in the opinion of the investigator continue to benefit from treatment with perampanel may opt to enroll into EAP (if activated), or temporarily into Extension B until EAP is activated or until perampanel is commercially available, whichever occurs first. At that point, the subject will complete his/her participation in Extension B. (revised per Amendment 04)

In the event that a risk-benefit assessment of perampanel for the treatment of LGS is found to be negative, this study will be terminated and no EAP will be set up. (revised per Amendment 04)

See [Appendix 4](#) for a full description of Extension B. (revised per Amendment 04)

The end of the study will be the date of the last visit of the last subject. (revised per Amendment 01)

9.2 DISCUSSION OF STUDY DESIGN, INCLUDING CHOICE OF CONTROL GROUPS

Randomization will be used in this study to avoid bias in the assignment of subjects to treatment, to increase the likelihood that known and unknown subject attributes (eg, demographics and baseline characteristics) are balanced across treatment groups, and to ensure the validity of statistical comparisons across treatment groups. Blinding to treatment will be used to reduce potential bias during data collection and evaluation of endpoints.

9.3 SELECTION OF STUDY POPULATION

Approximately 142 subjects will be randomized at approximately 70 sites in regions that include North America, Europe, and Asia. Approximately 30% of subjects will be recruited from the US. Sites will be encouraged to enroll subjects throughout the allowed age range (2 years and older). Subjects who do not meet all of the inclusion criteria or who meet any of the exclusion criteria will not be eligible to receive study drug.

9.3.1 Inclusion Criteria

Subjects must meet all of the following criteria to be included in this study:

1. Subjects must have diagnosis of LGS as evidenced by:
 - a. More than one type of generalized seizures, including drop seizures (atonic, tonic, or myoclonic) for at least 6 months before Visit 1

- b. An EEG reporting diagnostic criteria for LGS at some point in their history (abnormal background activity accompanied by slow, spike and wave pattern < 2.5 Hz)
2. Subjects must be at least 2 years old at the time of consent/assent
3. Subjects must have been <11 years old at the onset of LGS
4. Subjects must have experienced an average of at least 2 drop seizures per week in the 4-week Baseline Period preceding randomization; the Baseline Period within the Prerandomization Phase is (minimum) 4 weeks. (revised per Amendment 04)
5. Subjects must have been receiving 1 to 4 concomitant AEDs at a stable dose for at least 30 days before Visit 1 (vagal nerve stimulation [VNS] and ketogenic diet do not count as an AED). Use of cannabidiol (CBD) products is allowed and is counted as one of the 4 maximum allowed concomitant AEDs. CBD dose and product must have remained stable for at least 30 days before Visit 1 and is to remain the same throughout the course of the Core Study. (revised per Amendment 04)
6. In the investigator's opinion, parents or caregivers must be able to keep accurate seizure diaries
7. Body weight at least 8 kg

9.3.2 Exclusion Criteria

Subjects who meet any of the following criteria will be excluded from this study:

1. Presence of progressive neurological disease
2. Presence of drop seizure clusters where individual seizures cannot be reliably counted (seizure clusters are defined as ≥ 2 drop seizures with <5 minutes between any 2 consecutive seizures)
3. Prior treatment with perampanel with discontinuation due to safety issues (related to perampanel)
4. Prior treatment with perampanel within 30 days before Visit 1
5. Evidence of clinically significant disease (eg, cardiac, respiratory, gastrointestinal, renal disease, hepatic disease) that in the opinion of the investigator(s) could affect the subject's safety or study conduct
6. Scheduled for epilepsy-related surgery or any other form of surgery during the projected course of the study
7. Ketogenic diet and VNS, unless stable and ongoing for at least 30 days before Visit 1
8. Treatment with an investigational drug or device within 30 days before Visit 1
9. Status epilepticus within 12 weeks of Visit 1
10. If felbamate is used as a concomitant AED, subjects must be on felbamate for at least one year, with a stable dose for 60 days before Visit 1. They must not have a history of white blood cell (WBC) count below $\leq 2500/\mu\text{L}$ ($2.50 \times 10^9/\text{L}$), platelets < $100,000/\mu\text{L}$,

liver function tests >3 times the upper limit of normal (ULN), or other indication of hepatic or bone marrow dysfunction while receiving felbamate.

11. Concomitant use of vigabatrin: Subjects who took vigabatrin in the past must be discontinued for at least 5 months before Visit 1, and must have documentation showing no evidence of a vigabatrin-associated clinically significant abnormality in an automated visual perimetry test
12. Have had multiple drug allergies or a severe drug reaction to an AED(s), including dermatological (eg, Stevens-Johnson syndrome), hematological, or organ toxicity reactions
13. Evidence of significant active hepatic disease. Stable elevations of liver enzymes, alanine aminotransferase (ALT), and aspartate aminotransferase (AST) due to concomitant medication(s) will be allowed if they are < 3 times the ULN
14. Adrenocorticotrophic hormone within the 6 months before Visit 1
15. Had history of anoxic episodes requiring resuscitation within 6 months before Visit 1
16. Females who are breastfeeding or pregnant at Screening or Baseline (as documented by a positive beta-human chorionic gonadotropin [β -hCG] with a minimum sensitivity of 25 IU/L or equivalent units of β -hCG or hCG). A separate baseline assessment is required if a negative screening pregnancy test was obtained more than 72 hours before the first dose of study drug.
17. Females of childbearing potential who:
(revised per Amendment 01)
 - Within 28 days before study entry, did not use a highly effective method of contraception, which includes any of the following:
 - Total abstinence (if it is their preferred and usual lifestyle)
 - An intrauterine device or intrauterine hormone-releasing system (IUS)
 - An oral contraceptive (with additional barrier method if using contraceptive containing levogesterol) (Subject must be on a stable dose of the same oral contraceptive product for at least 28 days before dosing and throughout the study and for 28 days after study drug discontinuation.)
 - Have a vasectomized partner with confirmed azoospermia.
 - Do not agree to use a highly effective method of contraception (as described above) throughout the entire study period and for 28 days after study drug discontinuation.

For sites outside of the EU, it is permissible that if a highly effective method of contraception is not appropriate or acceptable to the subject, then the subject must agree to use a medically acceptable method of contraception, ie, double-barrier methods of contraception such as condom plus diaphragm or cervical/vault cap with spermicide. (revised per Amendment 01)

(NOTE: All females will be considered to be of childbearing potential unless they are postmenopausal [amenorrheic for at least 12 consecutive months, in the appropriate age group, and without other known or suspected cause] or have been sterilized surgically [ie,

bilateral tubal ligation, total hysterectomy, or bilateral oophorectomy, all with surgery at least 1 month before dosing]).

18. Had intermittent use of benzodiazepine of more than 4 single administrations in the month before Visit 1
19. A prolonged QT/QTc interval (QTc >450 ms) as demonstrated by a repeated electrocardiogram (ECG)
20. Hypersensitivity to the study drug or any of the excipients
21. Any history of a medical condition or a concomitant medical condition that in the opinion of the investigator(s) would compromise the subject's ability to safely complete the study
22. Known to be human immunodeficiency virus (HIV) positive
23. Active viral hepatitis (B or C) as demonstrated by positive serology at Screening
24. Psychotic disorder(s) or unstable recurrent affective disorder(s) evident by use of antipsychotics or prior suicide attempt(s) within approximately the last 2 years
25. History of drug or alcohol dependency or abuse within approximately the last 2 years; use of illegal recreational drugs
26. Concomitant use of medications known to be inducers of cytochrome P450 (CYP3A) including, but not limited to: rifampin, troglitazone, St John's Wort, efavirenz, nevirapine, glucocorticoids (other than topical usage), modafinil, pioglitazone, and rifabutin.
27. Use of AEDs not recommended by Epilepsy Treatment Guidelines for use in LGS including, but not limited to carbamazepine, gabapentin, oxcarbazepine, phenytoin, pregabalin, tiagabine, and vigabatrin (revised per Amendment 02)
28. Any suicidal ideation with intent with or without a plan within 6 months before Visit 2 (ie, answering "Yes" to questions 4 or 5 on the Suicidal Ideation section of the C-SSRS) in subjects aged 8 and above. (revised per Amendment 01)
29. Subjects with rare hereditary problems of galactose intolerance, the Lapp lactase deficiency or glucose-galactose malabsorption. (revised per Amendment 04)

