| Urine drug testing ^o | X | | | | | | | | | | |
| Dispense/collect seizure diary | X | X | X | X | X | X | X ^p | X | X | X | (X) ⁱ |
| IxRS | X | X | X | X | X | X | X | X | | X | (X) ⁱ |
| Dispense study drug | | X | X | X | X | X | X | | | | (X) ⁱ |
| Administer study | | | | | X ^r | X ^r | | | | | |

Table 5 Schedule of Procedures/Assessments in Study E2007-G000-338 (Core Study)

(revised per Amendments 01, 04, and 05)

| Phase | Prerandomization | Randomization | | | | | | | | | |
|--|---------------------|------------------------|---|----|--------------------------|----------------|----------------|----------------|--------------------------------|---------------------------------|------------------|
| Period | Screening/Base line | Titration ^a | | | Maintenance ^b | | | Early DC | Follow-up | | Unscheduled |
| Visit | 1 ^a | 2 ^c | 3 | 4 | 5 | 6 | 7 ^d | | Follow-up, 1 week ^e | Follow-up, 4 weeks ^e | |
| Week | (up to -8) | 1 | 2 | 4 | 7 | 13 | 19 | | 20 | 23 | |
| Day | (up to -56) | 1 | 8 | 22 | 43 | 85 | 127 | | 134 | 155 | |
| Procedures/ Assessments | | | | | | | | | | | |
| drug at site | | | | | | | | | | | |
| Retrieve unused study drug | | | X | X | X | X | X | X | | | (X) ⁱ |
| Adverse events | X | X | X | X | X | X | X | X | X | X | X |
| CCI | | | | | | | | | | | |
| Perampanel blood concentration samples | | | | | X ^r | X ^r | X ^s | X ^s | X ^s | | (X) ⁱ |
| CGI-S | | X | | | | | | | | | |
| CGI-I | | | | | | | X | X | | | (X) ⁱ |
| Pharmacogenomic blood samples ^t | | X | | | | | | | | | |

Footnotes for Table 5:

AED = antiepileptic drug; CGI-I = Clinical Global Impression of Improvement; CGI-S = Clinical Global Impression of Severity; C-SSRS = Columbia Suicide Severity Rating Scale; DC = discontinuation; ECG = electrocardiogram; EEG = electroencephalogram; CCI [REDACTED] HBsAg = Hepatitis B surface antigen; HepC = Hepatitis C; CCI [REDACTED] PK = pharmacokinetic

- a: Visits will have a window of ± 3 days with at least 10 days between visits (with the exception of Visit 3).
- b: Visits will have a window of ± 6 days.
- c: There must be at least 4 weeks between Visits 1 and 2.
- d: For those subjects who have completed Visit 7 study assessments and who are rolling over into Extension A, Visit 7 will serve as the End-of-Core Study visit and the beginning of the blinded Conversion Period of Extension A. (revised per Amendments 04 and 05)

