- e: Only for those subjects not rolling over into Extension A, and for those subjects who prematurely discontinued from the study, the Follow-up visits will take place at 1 week and 4 weeks after the last study drug administration (ie, Visit 7 or Early Discontinuation Visit, respectively). These visits will not be conducted if the subject continues into Extension A, in which case, a Follow-up visit will be performed 4 weeks after the last Extension visit. Visits will have a window of ± 6 days. (revised per Amendments 01 and 04)
- f: Final determination of eligibility and, if eligible, randomization to occur before any study drug administration. (revised per Amendment 04)
- g: Lifetime AED history will be collected as part of medical history.
- h: Height of adult subjects is to be recorded only at the Screening Visit (Visit 1). (revised per Amendment 01)
- i: CCI [REDACTED]
- j: [REDACTED]
- k: Subjects ≥ 8 years of age at time of informed consent/assent and subjects who will reach the age of 8 years during the double-blind phase of the study will also be assessed using the C-SSRS starting at Baseline. (revised per Amendment 03)
- l: Urine and serum pregnancy testing is for postpuberty, premenopausal females and postmenopausal females who have been amenorrheic for less than 12 months.
- m: Clinical laboratory tests include chemistry, hematology, and urinalysis. If a urine sample cannot be obtained; the subject will still be eligible for enrollment. However, every effort should be made to collect a sample.
- n: Fasting samples to be taken at indicated time points for glucose and lipid panel.
- o: Drug screen includes cocaine, phencyclidine [(PCP)], opioids ([as a group]), benzodiazepines, barbiturates, and amphetamines. Positive CBD results in subjects taking CBD products will not be exclusionary. (revised per Amendment 04)
- p: Collect diaries at Visit 7 from subjects not rolling over into Extension A. Dispense diaries at Visit 7 to subjects rolling over into Extension A.
- q: CCI [REDACTED]

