| Urine pregnancy test ^f | X | X | X | X | X | X | X | X | X | (X) ^e |
| Clinical laboratory tests ^g | X ^g | | X | | X | | X ^h | X ^h | X | (X) ^e |
| CCI | | | | | | | | | | |
| C-SSRS | | | X | X | X | X | X | X | X | (X) ^e |
| Dispense/collect seizure diary | X | X | X | X | X | X | X | X | | (X) ^e |
| IxRS | X | X | X | X | X | X | | | | (X) ^e |
| Dispense study drug | X | X | X | X | X | X | | | | (X) ^e |
| Retrieve unused study drug | X | X | X | X | X | X | X | X | | (X) ^e |
| Adverse events | X | X | X | X | X | X | X | X | X | X ^c |

bpm = beats per minute; C-SSRS = Columbia Suicide Severity Rating Scale; DC = discontinuation; EEG = electroencephalogram, F/U = Follow-up; IxRS = interactive voice and web response system.

- a: Extension A begins with Week 19 after the completion of end of Core Study Visit (Visit 7) assessments. That is, for those subjects rolling over into Extension A, Visit 7 (Week 19) will mark the end of the Core Study and the beginning of the blinded Conversion Period of Extension A. (revised per Amendment 04)
- b: Conversion Period visits (Visits 8 and 9 of Extension A) will have a window of ±3 days with at least 10 days between visits
- c: Visit will have a window of ±6 days
- d: Systolic blood pressure, diastolic blood pressure, heart rate (bpm), height, and weight (kg). Height of adult subjects is to be recorded only at the Screening Visit (Visit 1). (revised per Amendment 01).
- e: Unscheduled procedures to be conducted as needed. (revised per Amendment 04)
- f: Urine pregnancy testing is for postpuberty, premenopausal females and postmenopausal females who have been amenorrheic for less than 12 months. (revised per Amendment 04)
- g: Clinical laboratory tests include chemistry, hematology, and urinalysis.
- h: Fasting samples to be taken at indicated time points for glucose and lipid panel
- i: **CCI**

Table 9 presents the blood volumes to be collected during Extension A. The total volume of blood taken in Extension A for subjects who complete all visits will be 30 mL. For subjects who complete both the core study and Extension A, the blood volume will be 66 mL (not including unscheduled visits). (revised per Amendment 04)

Table 9 Blood Volumes Taken During Extension A (revised per Amendment 04)

| Visit No. | Visit 8 | Visit 10 | Visit 12 | Visit 14 | Early Discontinuation | Follow-up Visit | Unscheduled Visit |

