5.6.6 Other Safety Analyses

5.6.6.1 C-SSRS

Scoring of the C-SSRS will be performed as suggested by the C-SSRS Columbia website http://www.cssrs.columbia.edu/clinical_trials.html.

The following summaries will be presented for the treatment duration (defined as the period from the date of first dose up to 28 days after the date of last dose, inclusive).

- Number (percentage) of subjects with any treatment-emergent report of suicidal behavior, suicidal ideation, and suicidality (suicidal behavior and/or ideation) will be displayed. A treatment-emergent report of suicidal behavior, suicidal ideation, or suicidality is an answer of 'Yes' to any question in the respective category during the treatment duration.
- Shift from baseline to the maximum suicidal ideation severity rating (0=no ideation present to 5=active ideation with plan and intent) in the treatment duration will assess worsening of suicidal ideation. Any score greater than 0 indicates the presence of suicidal ideation while a score of 4 (active suicidal ideation with some intent to act) or 5 (active suicidal ideation with specific plan and intent) can be used to indicate serious suicidal ideation.

Descriptive statistics and changes from baseline will be presented by visit for the suicidal ideation severity rating (treated as a continuous variable) to assess change in suicidal ideation over time.
Other Analyses

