8.2 SAFETY DATA HANDLING

8.2.1 Baseline safety

The baseline value for all safety endpoints will be the last non-missing measurement occurring prior to the first dose of the study medication.

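### Exclusion 28 rests on C-SSRS items up to Visit 2, but the only pre-dose C-SSRS scheduled in Table 5 is at Visit 1, 28 to 56 days earlier

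*Protocol*

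**What the plan says.** **Criterion.** Exclusion 28 (Protocol 9.3.2, repeated in the Synopsis) covers "Any suicidal ideation with intent with or without a plan within 6 months before Visit 2" in subjects aged 8 and above. It defines this as a Yes to ideation question 4 or 5 of the C-SSRS. It is the only exclusion that counts back from Visit 2. The others that count back from a numbered visit (4, 7, 8, 9, 10, 11, 14, 15 and 18) use Visit 1.

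**When eligibility is settled.** Table 5 marks the inclusion/exclusion check at Visit 1 and again at Visit 2. Note f, attached to the Visit 2 mark, reads "Final determination of eligibility and, if eligible, randomization to occur before any study drug administration". Protocol 9.1.2 lets only subjects who still satisfy the criteria enter titration.

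**Timing.** Note c to Table 5 says "There must be at least 4 weeks between Visits 1 and 2". Protocol 9.1.1.1 allows screening to begin as early as Day -56.

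**C-SSRS schedule.** The C-SSRS row of Table 5 is marked at Visit 1 and is blank at Visit 2. The Synopsis, Protocol 9.5.1.5 and note k say that assessment begins at Baseline and give no visit number. In the Synopsis and 9.5.1.5 that wording is attached to subjects who will turn 8 during the double-blind phase. Note k applies it to those already 8 as well.

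**Analysis.** SAP 8.2.1 states "The baseline value for all safety endpoints will be the last non-missing measurement occurring prior to the first dose of the study medication". SAP 5.6.6.1 uses that baseline for the "Shift from baseline to the maximum suicidal ideation severity rating" and for by-visit changes. Its on-treatment window is "the period from the date of first dose up to 28 days after the date of last dose, inclusive".

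**The concern.** The criterion names both an instrument and an end date, but the instrument is not scheduled at that date. A subject whose ideation with intent begins after Visit 1 meets exclusion 28 at Visit 2. No scheduled C-SSRS would show it, so detection depends on how the investigator carries out the Visit 2 check.

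The protocol treats another ageing screening result differently. For pregnancy, exclusion 16 says "A separate baseline assessment is required if a negative screening pregnancy test was obtained more than 72 hours before the first dose", and Table 5 marks a urine test at Visit 2.

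The same Visit 1 rating becomes the SAP baseline. If ideation worsens between Visit 1 and first dose and persists, the shift table will show it as worsening on treatment.

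**Working it through.** The plan states no figure for this point. The check is a reading of the table and calendar arithmetic.

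**1. Is Visit 2 really blank?** The C-SSRS row has 11 cells: X, four blanks, X, blank, X, blank, X, (X).
- Against the Week and Day rows, Visit 2 (Day 1) is cell 2: blank.
- The Visit header in the upper part of the table is shifted by one cell. Against that header, Visit 2 is cell 3: also blank.
- The rows for vital signs, laboratory tests and CGI-S also have 11 cells, and each has a mark in cell 2. The blank is therefore not a visible shift of the row.

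**2. Age of the last scheduled rating at final eligibility.**
- Minimum: 4 weeks × 7 = 28 days (note c).
- Maximum: Day -56 to Day 1 = 56 days (Protocol 9.1.1.1).

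**3. Share of the look-back with no scheduled rating.** Taking 6 months as 183 days:
- 28 / 183 = 15%
- 56 / 183 = 31%

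**4. Spacing of scheduled ratings across first dose, on nominal days.**
- Read against the Week and Day rows, the next rating is on Day 85, which is 84 days after Day 1: 28 + 84 = 112 to 56 + 84 = 140 days.
- Read against the shifted header, it is on Day 43, which is 42 days after Day 1: 28 + 42 = 70 to 56 + 42 = 98 days.

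**5. Which visit is Baseline?** The documents point both ways.
- Visit 1: Table 5 heads that column Screening/Baseline.
- Visit 2: note a to Table 2 asks for fasting samples at Baseline, and Table 5 places the first of them at Visit 2. SAP 8.1.1 equates baseline with Visit 2. Exclusion 16 separates Screening from Baseline.

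If Baseline means Visit 2, the text asks for a rating that the table omits. If it means Visit 1, the 28 to 56 day gap follows. Table 5 or its wording needs correction either way.

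**6. What the old baseline affects.** The main C-SSRS summary counts subjects with any Yes during the treatment window and makes no use of baseline. Only the shift table and the change-from-baseline summaries use it. Both are descriptive, and the timing is the same in both arms.

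**7. With a Visit 2 rating that covers the time since Visit 1.** The unrated part of the look-back falls from 28–56 days to 0. The interval in step 4 splits into 28–56 and 84 days (or 28–56 and 42).

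**The case against.** **The Visit 2 check already covers this.** Inclusion/exclusion is marked at Visit 2, and exclusion 28 states its own two questions, so an investigator confirming eligibility has to address them up to that date. Adverse events are also collected at Visit 2, unscheduled ratings are possible, and Protocol 9.3.3 withdraws high-risk subjects on the C-SSRS, clinical impression or both. This stands, and it limits the point. A reader might infer that subjects with recent intent will pass unnoticed. The documents do not support that. What is missing is the scheduled rating, not the eligibility check.

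**Other screening tests are not repeated either.** The ECG, viral serology and urine drug screen are marked only at Visit 1. That is true, so the pregnancy test is only an analogy. But the exclusions those tests serve are not tied to Visit 2, and exclusion 28 is.

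**The safety comparison is unbiased.** This also stands. A reader might infer that the old baseline distorts the comparison between arms. It affects both arms in the same way, and only in descriptive displays.

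**The table was read by machine.** Read against the Week and Day rows, the C-SSRS also looks blank at Visit 7, and a reader might infer that there is no end-of-treatment rating. The documents do not support that. The other 10 legible rows marked at Early Discontinuation are all marked at Visit 7, and under the shifted header the C-SSRS has a mark there. A lost mark or a misaligned column is the likelier explanation. The Visit 2 blank does not depend on this, because it appears on both readings, but the row should still be compared with the original table.

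**Conclusion.** The point holds as a minor one. The criterion is defined by C-SSRS items up to Visit 2, and the last scheduled rating before the decision is 28 to 56 days old, or 15% to 31% of the look-back. The wording about Baseline does not resolve this: it either conflicts with Table 5 or confirms the gap.

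The consequence is a weaker basis for one safety exclusion in subjects aged 8 and above, and an older baseline for descriptive C-SSRS displays. The primary endpoint, the key secondary endpoints, alpha and power are unaffected.

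The conclusion assumes that the Visit 2 cell is blank in the original table and that 6 months is about 183 days. The documents give no rate of new ideation between visits and no share of subjects aged 8 and above, so the number affected cannot be estimated. The percentages describe time without a rating, not risk.

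**What to change.** 1. Mark the C-SSRS at Visit 2 in Table 5, before randomization and dosing, covering the time since Visit 1, and apply exclusion 28 to that rating. Name the visit where the text now says only Baseline.
2. SAP 8.2.1 then takes the Visit 2 rating as baseline without change. Visit 2 is Day 1, however, and the SAP's C-SSRS window opens on the date of first dose. Add one sentence to SAP 5.6.6.1: a rating made before dosing on that date is baseline and is not treatment-emergent. Note a to the window tables in SAP 8.2.2 already does this for vital signs and laboratory tests.

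The cost is a few minutes at Visit 2 for subjects assessed with the C-SSRS, using a questionnaire already in the study at a visit they already attend. Protocol 11.1 requires a written amendment, and a change bearing on subject safety also goes to regulators and ethics committees. With about 70 sites it would best be included in an amendment that also carries other changes.
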